9.8 Analysis of exploratory MRI efficacy variables

9.8.1 Number of CUALs

The cumulative number of CUALs from baseline up to Weeks 24, 48, 72, 96 and EOT will be analyzed on the FAS using a negative binomial regression model: response variable is the cumulative number of CUALs up to each timepoint, with treatment as a factor and EDSS category (IRT) as a covariate, and the log of the time up to last MRI scan for the timepoint (in years) as an offset. Mean model-based estimates for the number of CUALs per subject per year, rate ratio, and corresponding 95% CIs will be presented.

The cumulative number of CUALs from baseline up to each timepoint will be summarized descriptively using the FAS. The total number of CUALs as well as the total cumulative time up to the last MRI scan at the timepoint (summed for all subjects) will also be displayed. From the total number of CUALs and the total cumulative time to the last MRI scan the raw number of CUALs per year will be calculated and summarized.

CUAL data will be listed on the FAS.

9.8.2 Number of T1 Gd+ lesions

The cumulative number of T1 Gd+ lesions up to Weeks 24, 48, 72, 96, EOT and EOS will be analyzed on the FAS using a negative binomial regression model, with the cumulative number of T1 Gd+ lesions up to the timepoint as the response variable, treatment as a factor, EDSS stratification category as a covariate, and the log of the number of included scans up to the timepoint as an offset. Mean model-based estimates for the number of T1 Gd+ lesions per subject per scan, rate ratio, and corresponding 95% CIs will be presented.

The cumulative number of T1 Gd+ lesions from baseline up to each timepoint will be summarized descriptively using the FAS. The total number of T1 Gd+ lesions as well as the total number of included scans (summed for all subjects) will also be displayed. From the total number of T1 Gd+ lesions and the total number of included scans the raw number of T1 Gd+ lesions per scan will be calculated and summarized. For the number of T1 Gd+ lesions from baseline up to EOS the frequency per category will also be presented (anticipated categories: 0, 1, 2, 3, 4+).

Descriptive summary statistics of the number of T1 Gd+ lesions at each scheduled visit will also be presented.

T1 Gd+ lesion data will be listed on the FAS.

9.8.3 Number of new or enlarging T2 lesions

The cumulative number of new or enlarging T2 lesions up to Weeks 24, 48, 72, 96, EOT and EOS will be analyzed on the FAS using a negative binomial regression model as described above in Section 9.8.1 for number of CUALs, with the cumulative number of new or enlarging T2 lesions up to the timepoint as the response variable.

The cumulative number of new or enlarging T2 lesions from baseline up to each timepoint will be summarized descriptively using the FAS. The total number of new or enlarging T2 lesions as well as the total cumulative time up to the last MRI scan at the timepoint (summed for all subjects) will also be displayed. From the total number of new or enlarging T2 lesions and the total cumulative time to the last MRI scan the raw number of new or enlarging T2 lesions per year will be calculated and summarized. For the number of new or enlarging T2 lesions from baseline up to EOS the frequency per category will also be presented (anticipated categories: 0, 1, 2, 3, 4+).

Descriptive summary statistics of the number of new or enlarging T2 lesions at each scheduled visit will also be presented.

T2 lesion data will be listed on the FAS.

9.8.1 Analysis of time to 24-week CDA

Analysis of time to 24-week CDA will be analyzed in the same way as analysis of time to 12-week CDA as described in Section 9.7.1.

9.8.2 Change in EDSS from baseline by visit up to EOS

The EDSS score and change from baseline in EDSS score by visit and treatment group will be summarized using descriptive statistics on the FAS. A listing of EDSS / FS scores will be produced on the FAS.

9.9 Analysis of safety variables

9.9.1 Adverse events

All AEs captured (i.e., from signature of informed consent up to EOS) are reported in the subject listings based on the SCR, treatment-emergent events are flagged.

Unless otherwise specified, the SAF is used for all analyses of AEs.

An overview of treatment-emergent AEs is presented, per treatment group, as the number and percentage of subjects having any AE, any severe AE, any drug-related AE, any AE leading to study drug discontinuation, any SAE, any drug-related SAE, or any fatal SAE.

Also, AEs are summarized by SOC and PT: Presenting, per treatment group, the number and percentage of subjects having any AE, having an AE in each primary SOC, and having each individual AE (PT). SOC's are sorted by descending order of frequency in the ponesimod arm. If the frequencies of SOC's are the same, alphabetical order is used. The same rule applies for PT's within SOC. The following summaries are presented:

- Treatment-emergent AEs
- Treatment-emergent AEs on Day 1
- Treatment-emergent AEs on Day 1 of re-initiation, for subjects with at least one re-initiation
- Treatment-emergent AEs leading to temporary interruption of study treatment
- Treatment-emergent AEs considered to be related to DMF
- Treatment-emergent AEs considered to be related to study drug
- Treatment-emergent AEs with fatal outcome

Also, treatment-emergent AEs are summarized by PT: presenting, per treatment group, the number and percentage of subjects having any AE, and having each individual AE (PT). PT's are sorted by descending order of frequency in the ponesimod arm. If the frequencies are the same, alphabetical order is used.

For the disclosure of the results to EudraCT and ClinicalTrials.gov (and inclusion in the CSR appendix), frequent treatment-emergent non-serious AEs, i.e., PT's reported in $\geq 5\%$ of subjects in at least one treatment group, are summarized as follows:

- 1) The number and percentage of subjects having any frequent non-serious AE, and having each individual non-serious AE (PT).
- 2) The overall number of frequent non-serious AEs (i.e., reported episodes), and the number and percentage of frequent AEs (PT). Here the denominator is the overall number of frequent non-serious AEs.

9.9.2 Deaths, other serious adverse events

9.9.2.1 Death

A separate listing including all deaths is provided based on the SCR; treatment-emergent deaths are flagged as such in that listing.

9.9.2.2 Serious adverse events

Unless otherwise specified, the SAF is used for all analyses of SAEs.

SAEs are summarized by SOC and PT. The following summaries are presented:

- Treatment-emergent SAEs
- Treatment-emergent SAEs on Day 1
- Treatment-emergent SAEs on Day 1 of re-initiation, for subjects with at least one re-initiation
- Treatment-emergent SAEs considered to be related to study drug

For the disclosure of the results to EudraCT and ClinicalTrials.gov (and for inclusion in the CSR appendix), the overall number of treatment-emergent SAEs (i.e., reported episodes), and the number and percentage SAEs (PT) are summarized. Percentages of subjects are based on the number of subjects in the safety analysis set and the percentages of events are based on the total number of events.

9.9.2.3 Treatment-emergent adverse events leading to study treatment discontinuation

The SAF is used for all analyses of AEs leading to discontinuation. AEs leading to premature discontinuation of study drug are summarized by SOC and PT. The following summaries are presented:

- Treatment-emergent AEs leading to premature discontinuation of study drug.

9.9.2.4 Other significant adverse events

9.9.2.4.1 Adverse events of special interest

For each of the AESI categories described in Section 5.5.9.1, the following information is presented: The number and percent of subjects with each AESI is summarized by PT per treatment arm. In addition, the number and percentage of subjects having any event of that category, having any serious event, any fatal event or any event leading to premature discontinuation is presented.

AESI are presented in a dedicated listing.

9.9.2.4.2 Major adverse cardiovascular events

A listing of MACE events is prepared.

9.9.3 Electrocardiography (ECG)

The following summary displays are provided by treatment group, all based on the SAF:

- Quantitative ECG results and absolute change from baseline, as described in Section 5.5.11.1, are summarized descriptively, by parameter and visit. Except for data summarized under ‘Baseline’, ‘last-on-treatment’ and ‘Day-30 follow-up’, only treatment-emergent results from nominal scheduled visits are included, premature EOT visit is mapped to a scheduled visit [see Section 11.3];
- Quantitative ECG results and absolute change from pre-dose on Day 1, by timepoint (pre-dose, 1–4 hours post dose), are summarized descriptively;
- Number and percentage of subjects with any treatment-emergent PR, QTcF prolongations and HR outliers are presented overall. Percentages are based on the number of subjects with at least one treatment-emergent result available for the corresponding parameter. Abnormalities are presented cumulatively, i.e., a subject with a treatment-emergent QTcF result > 500 ms is also summarized in the category QTcF > 450 ms;
- Number and percentage of subjects with any 3-hr post-dose PR, QTcF prolongations and HR outliers on Day 1, Week 12 Visit, and Day 1 of any re-initiation. For this analysis the ECG results reported as 3-hours post-dose are considered, irrespective of actual time the ECG was performed. Percentages are based on the number of subjects with a result available for the corresponding parameter at 3-hours post-dose. Abnormalities are presented cumulatively;
- Number and percentage of subjects with new treatment-emergent morphological ECG findings, by abnormality and group term following CDISC terminology are presented;
- Number and percentage of subjects with new treatment-emergent post-dose morphological ECG findings on Day 1 or on Day 1 of any re-initiation, by abnormality and group term following CDISC terminology are presented.

All ECG data including QTc parameters are listed by treatment group and subject based on the SCR. All marked abnormalities are flagged and morphological findings are listed.

9.9.4 Vital signs and body weight

The following summary displays are provided by treatment group, all based on the SAF:

- Blood pressure and body weight including absolute change from baseline, as described in Section 5.5.10, are summarized descriptively, by parameter and visit. Except for ‘Baseline’, ‘Last on treatment’ and ‘Day-30 follow-up’, only treatment-emergent results from nominal scheduled visits are included; premature EOT visit is mapped to a scheduled visit [see Section 11.3];
- Blood pressure including absolute change from baseline on Day 1, by timepoint (pre-dose, 1–4 hours post dose), are summarized descriptively;

- Number and percentage of subjects with any treatment-emergent blood pressure result meeting the criteria defined in Section 5.5.10.1. Percentages are based on the number of subjects with at least one treatment-emergent result available for the corresponding parameter;
- Number and percentage of subjects with post-dose blood pressure result on Day 1 meeting the criteria defined in Section 5.5.10.1 are presented overall post-dose hours. Percentages are based on the number of subjects with blood pressure results available for the corresponding parameter.

Unscheduled visits are not presented in summary tables by visit. Unscheduled assessments that meet the pre-defined high/low criteria will be flagged and may be included in the corresponding incidence tables.

All blood pressure as well as body weight, body temperature and pulse rate results are listed by treatment group and visit based on the SCR. A listing for blood pressure measurements in subjects with at least one treatment-emergent marked blood pressure abnormality will also be presented on SCR.

9.9.5 Laboratory tests

Descriptive summary statistics by visit and treatment group are provided for laboratory test results reported by the central laboratory and corresponding absolute changes from baseline, based on the SAF. Except for 'Baseline', 'Last on treatment' and 'Day-30 follow-up', only treatment-emergent results from nominal scheduled visits are included; premature EOT visit is mapped to a scheduled visit [see Section 11.3]. Data are displayed in SI units as provided by the central laboratory. Values from unscheduled visits are not included in by visit summaries but are included in the listings and in the summaries for marked abnormalities and liver function test abnormalities.

For lymphocyte counts, this table is also provided on percent changes from baseline. The number of subjects with at least one treatment-emergent marked laboratory abnormality is summarized by treatment group, based on the SAF. The worst case in each direction is considered and summarized in all applicable categories, i.e., a subject counted in LLL is also counted in LL for a given parameter; also, a subject maybe counted in both the high and the low category for a given parameter. In addition, the number of subjects with treatment-emergent liver function test abnormalities is summarized by treatment group. The denominator for percentages is the number of subjects with at least one post-baseline assessment.

Safety laboratory hematology, clinical chemistry, urinalysis parameters planned as per protocol are also presented in subject data listings based on the SCR. All abnormalities and marked abnormalities including those at baseline are flagged in the listings.

A shift table of the frequency counts and percentages of number of subjects with positive, negative and indeterminate results at baseline and at EOS for JCV serology will be presented separately.

Other laboratory parameters are presented in a separate listing on the SCR.

Further analyses related to lymphocytes and lymphocyte subsets are described in Section 9.10.

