5.5 Safety variables

5.5.1 Definition of treatment-emergent, baseline and change-from-baseline, last on treatment, follow-up assessments for safety variables

For all safety data analyses described in this SAP, baseline is considered to be the last valid assessment prior to first study drug intake. Assessments at Visit 1 (Screening) and Visit 2 (Baseline), with date on or prior to the date of first intake of study treatment, and with no time collected, are considered eligible for baseline.

For each individual safety variable, baseline is defined to be the last valid measurement available before the date and time of first dose intake of study treatment, unless otherwise specified. On days where study drug is initiated or re-initiated, the pre-dose assessment for that day is defined as the last non-missing assessment prior to the study drug intake on that day. The pre-dose assessment on Day 1 (if available) is identical to baseline; however, missing pre-dose data on Day 1 is not imputed with baseline. In case of (partially) missing assessment dates/times, or for assessments reported on Day 1 (or day of re-initiation) with recorded assessment time contradicting the timepoint label (e.g., pre-dose, 2 hours post-dose), the nominal visit and timepoint labels will be used to determine whether an assessment is considered for baseline (for example a blood pressure measurement with an assessment date on Day 1 but with a missing assessment time or an assessment time prior to the reported time of first study drug intake, will not be considered for

baseline if reported under the timepoint “2 hours post-dose” in the eCRF, however it will be considered if reported as “Pre-dose” in the eCRF).

Absolute changes from baseline are defined as post-baseline value minus baseline value, i.e., a positive sign indicates an increase compared to baseline.

A percentage change from baseline is defined as the absolute change from baseline divided by the baseline value (if the baseline value is > 0) and then multiplied by 100.

Absolute and percent change from baseline is calculated and stored for all continuous safety data.

In addition, the following assessments are flagged or derived per parameter:

- Last on-treatment assessment: Last assessment prior to or on EOT date +1 day (last on treatment may come from a scheduled or an unscheduled visit)
- Day-30 follow-up, between EOT + 16 days and EOT + 37 days [see Section 11.4]

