A safety assessment (ECG, vital signs, laboratory) is considered treatment-emergent, if the assessment date is on or after the study treatment start date and prior to or on the study treatment end date + 15 days (inclusive). If both, the assessment date/time and the date/time of study treatment start are available, only events with date/time on or after the date/time of study treatment start are considered to be treatment-emergent. In case of (partially) missing assessment dates/times, or for assessments on treatment Day 1 with reported assessment time contradicting the timepoint label, the nominal visit and timepoint labels will be used to determine whether an assessment is considered as treatment-emergent or not. For example, a blood pressure measurement with an assessment date on Day 1 but a missing assessment time or an assessment time after the time of first study drug intake, will not be considered treatment-emergent if reported under the timepoint “Pre-dose” in the eCRF, however it will be considered if reported as “2 hours post-dose” in the eCRF.

A safety event (AE, serious AE [SAE], Death) is considered treatment-emergent if the onset date/date of occurrence is on or after the study treatment start date and prior to or on the EOT date + 15 days (inclusive). Missing or partially missing onset or occurrence dates are imputed as described in Section 12.3. If both the onset/occurrence date/time and the date/time of study treatment start are available, only events with date/time on or after the date/time of study treatment start are considered to be treatment-emergent.

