5.5.12 Laboratory

Laboratory tests will be performed at Visit 1 (Screening), Visit 2 (Baseline), Visit 4 (Week 2), Visit 5 (Week 4), Visit 6 (Week 12) and every 12 weeks thereafter up to Visit 18 (EOT), and at Visit 20 (FU) and, if applicable, at all corresponding visits in the PTOP. Unscheduled laboratory tests may be performed at any time during the study (Visits U1, U2, U3, etc.).

Additional lymphocyte count measurements will be performed every 4 weeks up to Week 24.

Safety laboratory samples are centrally analyzed by Covance and the results are electronically transferred to Actelion. In exceptional cases, the protocol allows the utilization of local laboratories. Local laboratory analysis results are entered in the eCRF with some exceptions for blinding reasons (e.g., lymphocytes are not entered in the eCRF, see protocol). Quantitative results from local laboratories are not summarized (i.e., not included in summary statistics or graphical representations). Qualitative results like (marked) abnormality categorization, liver test elevation categories, etc. are derived from local laboratory data and summarized together with qualitative results derived from central laboratory data.

Safety laboratory hematology, clinical chemistry and urinalysis comprise the following parameters planned as per protocol:

Hematology: Red blood cell count, Total and differential WBC counts (basophils, eosinophils, lymphocytes, monocytes, neutrophils, band forms), Platelet count, Hemoglobin, Hematocrit.

Liver function tests and coagulation: International normalized ratio (INR), alanine aminotransferase (ALT), aspartate aminotransferase (AST), (alkaline phosphatase) AP, total bilirubin (TBIL).

Clinical chemistry (excl. liver tests): Lactate dehydrogenase, Creatinine, creatinine clearance (calculated by the central laboratory using Cockcroft-Gault), Blood Urea Nitrogen, Urate, Glucose, Total cholesterol, Triglycerides, Sodium, potassium, chloride, calcium, Total protein, albumin, C-reactive protein.

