9.9.7 Columbia Suicide ideation or behavior

Suicidal Ideation, Suicidal Behavior or Self-Injurious Behavior without Suicidal Intent will be listed for each patient, at each assessment visit on the SCR. Events occurring during the period up to EOT + 15 days (treatment-emergent period) will be flagged.

Number (%) of subjects with suicidal ideation (overall and by category), suicidal behavior (overall and by category), suicidal ideation score ≥ 4 or suicidal behavior and/or self-injurious behavior without suicidal intent will be tabulated by treatment group up to EOT + 15 days (worst outcome). Analyses will be based on subjects in the SAF who have at least one treatment-emergent eC-SSRS[®] measurement available.

For subjects who have in addition a baseline eC-SSRS[®] assessment available shifts from baseline (maximum score from pre-treatment recent history) to the worst reported outcome (the maximum score) up to EOT + 15 days will be tabulated by treatment group to demonstrate any changes in Suicidal Ideation and Suicidal Behavior score categories.

All eC-SSRS[®] data will be presented in a listing on SCR.

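### Laboratory abnormality percentages pair a treatment-emergent numerator with an any-post-baseline denominator, so they can be slightly understated and never overstated

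*SAP*

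**What the plan says.** Section 9.9.5 defines two numerators. For marked abnormalities: "The number of subjects with at least one treatment-emergent marked laboratory abnormality is summarized by treatment group, based on the SAF". For liver tests: "the number of subjects with treatment-emergent liver function test abnormalities is summarized by treatment group". The divisor that follows is: "The denominator for percentages is the number of subjects with at least one post-baseline assessment".

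Section 5.5.1 closes the treatment-emergent window for laboratory assessments: a result counts if dated on or after treatment start and "prior to or on the study treatment end date + 15 days (inclusive"). The follow-up assessment lies after that limit: "Day-30 follow-up, between EOT + 16 days and EOT + 37 days". Section 5.5.12 schedules laboratory tests at Weeks 2, 4 and 12, every 12 weeks up to the end-of-treatment (EOT) visit, and also "at Visit 20 (FU) and, if applicable, at all corresponding visits in the PTOP".

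For treatment-emergent ECG outliers, section 9.9.3 says: "Percentages are based on the number of subjects with at least one treatment-emergent result available for the corresponding parameter". Sections 9.9.4 (blood pressure) and 9.9.6 (spirometry) apply the same rule to their treatment-emergent tables. Section 9.9.7 (suicidal ideation or behavior) is similar: "Analyses will be based on subjects in the SAF who have at least one treatment-emergent" measurement.

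**The concern.** The numerator has an upper time limit and the denominator has none. A subject with laboratory results only at follow-up or in the PTOP adds one to the divisor but can never add one to the count, whatever those results show. Such a subject was not observed during the period the table describes, so counting them as free of a treatment-emergent abnormality dilutes the incidence.

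The sentence also lacks the restriction to the corresponding parameter that the ECG, blood pressure and spirometry sections carry. It can be read per parameter or across the whole laboratory panel, and two programmers could produce different denominators. The question is most pointed for the combined liver criteria in section 5.5.12.1, several of which need more than one analyte on the same sample date.

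At stake is the accuracy of descriptive safety percentages, including the liver tables, where any error should not run towards understating risk. No hypothesis test depends on them.

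**Working it through.** The SAP states no figure for this point, so there is nothing to reproduce. The check sets the windows side by side and then sizes the effect.

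**Windows**

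| Element | Time limits | Source |
|---|---|---|
| Numerator | treatment start to EOT + 15 days | 5.5.1 |
| Denominator | any time after baseline | 9.9.5 |
| Day-30 follow-up sample | EOT + 16 to EOT + 37 days | 5.5.1, 11.4 |
| PTOP samples | after EOT and follow-up | 5.5.12, Table 4 |

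The last two rows fall outside the numerator's window and inside the denominator's. Section 4.1 records that the treatment-emergent period was shortened from 30 to 15 days after discontinuation. A follow-up sample taken 16 to 30 days after the last dose is therefore now outside the numerator while still being post-baseline.

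**Direction.** Let N be the subjects in the planned denominator, k those among them with no treatment-emergent result, and x the subjects with a treatment-emergent abnormality.

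- Planned percentage: 100 × x/N
- Matched percentage: 100 × x/(N − k)
- Planned divided by matched: (N − k)/N, so the relative understatement is k/N

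Since k cannot be negative, the planned figure is equal to or below the matched one. At k = 0 they agree.

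**Size.** Section 2 gives 136 randomized subjects at a planned 1:1 ratio. I assume 136/2 = 68 per arm, all with a post-baseline laboratory assessment. The values of k and x are illustrative, because the SAP gives neither. With x = 7 the planned figure is 7/68 = 10.29%.

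| k | k/N | Matched percentage | Difference (points) |
|---|---|---|---|
| 0 | 0% | 10.29% | 0 |
| 1 | 1.5% | 7/67 = 10.45% | 0.15 |
| 2 | 2.9% | 7/66 = 10.61% | 0.31 |
| 3 | 4.4% | 7/65 = 10.77% | 0.48 |
| 7 | 10.3% | 7/61 = 11.48% | 1.18 |

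The absolute gap grows with the incidence: for x = 34 (planned 50.0%), k = 3 gives 34/65 = 52.3%, a gap of 2.3 points. For scale, one subject in 68 is 1.47 points.

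**The case against.** The strongest reply is that k will be close to zero. Blood is drawn at Weeks 2 and 4 and at EOT. Table 3 gives the EOT visit a window of + 7 days, well inside EOT + 15 days, so even a subject who stops in the first week is due a sample that counts as treatment-emergent. Attachment 1 lists a missed EOT visit as an important deviation. Unscheduled values enter the abnormality tables (9.9.5), and so do categories derived from local laboratory results (5.5.12). To fall into k, a subject must miss every usable on-treatment and EOT sample and still return later. This stands and limits the size of the effect. It does not remove the mismatch, since the deviation list itself provides for missing blood assessments and missed EOT visits.

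It is also fair that the denominator sentence may be meant per parameter: the surrounding paragraph speaks of a given parameter. The missing phrase is therefore an ambiguity, and a panel-wide denominator is only one reading.

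A reader might infer three stronger things, none of which the SAP supports:

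- **That the percentages are necessarily understated.** This requires k > 0, which is not known.
- **That the bias differs between arms, following early discontinuation.** Early stopping alone does not create the mismatch, because the EOT sample is still due. The SAP gives no ground for expecting k to differ by arm.
- **That laboratory tables are out of line with all other safety tables.** The SAP has no single convention. SAE percentages of subjects use the safety analysis set (9.9.2.2), the 3-hour ECG and Day 1 blood pressure tables use available results, the morphological ECG bullets state no denominator, and the lymphocyte criteria in 9.10.1 have their own. The contrast holds for the treatment-emergent ECG outlier, blood pressure and spirometry tables, with the suicidality table following the same principle.

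**Conclusion.** The point holds as a minor inconsistency. The denominator in 9.9.5 is wider than the period its numerator covers, and any resulting error goes one way, towards lower incidence. Under the assumption of about 68 per arm, 1 to 3 affected subjects would shift an incidence near 10% by 0.15 to 0.48 points, which is less than the weight of a single subject. The true shift may be nil. The tables are descriptive and the subject counts are unaffected, so no conclusion of the synoptic report should turn on this. It is worth correcting because the wording can only understate safety findings, leaves the per-parameter question open, and departs from the rule the SAP already uses for the closest comparable tables.

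**What to change.** In section 9.9.5, define the denominator for marked abnormalities and single-test liver abnormalities as subjects in the safety analysis set with at least one treatment-emergent result for the corresponding parameter. For the combined liver criteria in 5.5.12.1, define it as subjects in that set with at least one treatment-emergent sample date on which all component tests are available. The combined criteria need their own wording, because copying the ECG sentence would leave the corresponding parameter undefined for them.

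The cost is one or two sentences in the SAP and a change to the denominator flag in the programs for these tables. No additional data are needed. Showing the denominator for each parameter beside the percentage would let a reader see how many subjects had no treatment-emergent result.
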